9.3 Setting

The study will be conducted at Kaiser Permanente Southern California (KPSC), the largest managed care organization in Southern California, serving over 3.7 million members that are broadly representative of the diverse racial, ethnic and socioeconomic background of the source population in Southern California.[8] The racial/ethnic breakdown of the KPSC population is 41% Hispanic, 36% Non-Hispanic White, 11% Asian/Pacific Islander, 9% Black, and 3% other.

Prepaid, comprehensive health care is provided to KPSC members at 14 medical centers and over 200 satellite clinics. All health care encounters are tracked through electronic data systems, with detailed information on diagnoses applied, procedures performed, and

immunizations administered, regardless of setting. KPSC members may seek emergency medical care from outside health care providers. For outside providers to be reimbursed by the health plan for covered emergency care, claims have to be submitted with documentation of the episode of care, and that information is entered into the administrative data systems. Thus, the capture of care delivered to KPSC members by electronic data is very comprehensive.

KPSC health plan members can enroll through their employer or the employer of a family member, through individual and family plans, or through state or federal programs such as California Public Employees' Retirement System, MediCal, and Medicare.

The KPSC Regional Immunization Practice Committee (RIPC) makes recommendations to ensure appropriate use of vaccination and implementation of new ACIP immunization recommendations within KPSC. KPSC has a proactive immunization program that includes: 1) alerts in the electronic medical record that indicate which age-appropriate routine vaccines are due based on vaccines that the member has already received, 2) a policy of vaccinating at all visits, not just well child or physical exam appointments, and 3) giving immunizations on a walk-in basis without appointment and at no-cost nurse visits. Since there is no charge for immunizations for KPSC members, there is an incentive to receive immunizations within the KPSC system.

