Plan Prepared by: PPD, MS
Research Manager, Biostatistics
Kaiser Permanente Southern California

Version and Date: Version 2.0: 17 November 2015

Approvals

Approvers, Organization & Role	Approval Status	Date
PPD [REDACTED], MS KPSC Research and Evaluation Research Manager, Biostatistics	Approved	11/17/2015
PPD [REDACTED] KPSC Research and Evaluation Principal Investigator	Approved	11/17/2015
PPD [REDACTED] Department of Epidemiology GlaxoSmithKline Epidemiologist	Approved	11/17/2015

Publication Record

Version	Date	Primary Author	Description
1.0	September 18, 2015	PPD [REDACTED]	1 st Draft for GSK Review
1.1	October 16, 2015	PPD [REDACTED]	2 nd Draft for GSK Review
1.2	October 30, 2015	PPD [REDACTED]	Final draft for GSK Review
1.3	November 6, 2015	PPD [REDACTED] [REDACTED]	Comments on Draft 1.2
1.4	November 11, 2015	PPD [REDACTED]	Final draft for GSK Review
2.0	November 17, 2015	PPD [REDACTED]	Approvals obtained, SAP finalized

Definitions

Concomitant vaccination(s) – any other vaccination(s) administered to a subject on the same date as a MenACWY-CRM vaccination.

Day 0 - For the calculation of study day, Day 0 is the date when the index vaccination is received.

Event – Events are classified on an encounter level and a diagnosis level. For encounters, an inpatient admission, emergency department (ED) visit, or an ED visit resulting in an inpatient admission will each be treated as a single event. For diagnoses, all medical diagnoses made during ED and inpatient visits are considered events, which will be further classified as pre-existing, new, recurrent, or part of an ongoing episode.

Episode – Diagnosis-type medical events that result in multiple encounters during the observation period are considered episodes. Episodes comprise the course of a disease or condition, from initial presentation through resolution, as determined through chart review. An episode will be consolidated as a single event for analysis. For each episode, the first diagnosis date in any care setting will be used for analyses.

First-dose - no prior dose of a quadrivalent meningococcal conjugate vaccine recorded in the full medical history

Index vaccination – The first receipt of MenACWY-CRM at a KPSC facility between July 1, 2014 and June 30, 2017 in a study subject of which the date of administration defines the start of the observation period.

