5.2 Frequency and rate of events

The frequency of medical events is defined as the total number of each individual event. The frequency will be described by absolute number of each individual medical event and percentage of each individual medical event out of the total number of captured medical events during the observation period and included for analysis (as per Tables 4a or 4b).

The rate of medical events is defined as the number of all captured events divided by the total person-time following MenACWY-CRM doses administered during the study period. The rate and Poisson 95% confidence interval of the rate of medical events will be calculated and presented as number per 1000 person-years using SAS PROC GENMOD.

If the number of medical events allows, captured medical events will be stratified by dose and by the status of the diagnosis as first occurrence or recurrence. Person-time for each dose will begin at the date of vaccination and end at 6 months following vaccination, disenrollment, death, the end of data collection, or receipt of an additional dose of MenACWY-CRM, whichever comes first.

Frequency and rate of events will be characterized two ways: by encounter (hospitalization only, ED only, or both ED and hospitalization) and by diagnosis (see Appendix A, Table Shell 5 for details). For the analysis by encounter, the encounter date will be used to determine the timing of the encounter relative to the timing of vaccine dose. For the analysis by diagnosis, the first diagnosis date for each diagnosis in any care setting will be used to determine the timing of the diagnosis relative to the timing of vaccine dose. The analysis by diagnosis will be stratified by setting of diagnosis and recurrence when the number of events in each stratum is ≥ 5 . The setting of diagnosis reflects whether the diagnosis was captured by automated search in the inpatient setting, ED setting, or both. If possible, diagnoses will be grouped by category, and the frequency and rate of diagnoses will be presented by category.

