Appendix B: Underlying condition of vaccine indication

Vaccine recipients will be determined to have the following underlying conditions for vaccination if the associated diagnosis codes are present in the medical record six months prior to index vaccination, including the date of index vaccination.

1. Asplenia

Functional - Hemoglobinopathies (primarily sickle cell [SS or SC] disease)

ICD-9 Codes:

Diagnosis	ICD-9 Diagnostic Code
Sickle cell disease unspecified	282.60
HB-SS disease with crisis	282.62
Sickle cell thalassemia without crisis	282.41
Sickle cell/HB-C disease without crisis	282.63
Sickle cell/HB-C disease with crisis	282.64
Other sickle cell disease without crisis	282.68
Other sickle cell disease with crisis	282.69
Sickle cell thalassemia with crisis	282.42

ICD-10 Codes:

Diagnosis	ICD-10 Diagnostic Code
Sickle cell disease without crisis	D57.1
HB-SS disease with crisis, unspecified	D57.00
Sickle cell thalassemia without crisis	D57.40
Sickle cell/HB-C disease without crisis	D57.20
Sickle cell/HB-C disease with crisis, unspecified	D57.219
Other sickle cell disorders without crisis	D57.80

Other sickle cell disease with crisis, unspecified	D57.819
Sickle cell thalassemia with crisis, unspecified	D57.419
Hyposplenism	D73.0

Anatomic Asplenia

ICD-9 Codes:

Diagnosis	ICD-9 Diagnostic Code
Anomalies of spleen congenital	759.0

ICD-10 Codes:

Diagnosis	ICD-10 Diagnostic Code
Asplenia (congenital)	Q89.01
Congenital malformations of spleen	Q89.09
Acquired asplenia	Z90.81

2. Persistent Complement Component Deficiencies

ICD-9 Codes:

Diagnosis	ICD-9 Diagnostic Code
Other specified disorders involving the immune mechanism	279.8

ICD-10 Codes:

Diagnosis	ICD-10 Diagnostic Code
-----------	------------------------

Defects in the complement system	D84.1
----------------------------------	-------

Table 1: Study population selection

Population	Total (n)
Total number of persons within the KPSC cohort	
Total number of children 2-23 months old in the KPSC cohort	
Total MenACWY-CRM vaccine recipients among age 2-23 months	

Date tables created:

Period captured in the tables:

Report integrates the tables:

Table 2: Baseline Characteristics of MenACWY-CRM Recipients 2 to 23 Months of Age

Characteristic	Total	Number of doses received			
		One	Two	Three	Four
Age at first vaccination (months)	mean (sd) median Q1, Q3 (min - max)				
Age 2-6 months at first vaccination	n (%)				
Age 7-23 months at first vaccination	n (%)				
Gender					
Male	n (%)				

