Number of recipients experiencing multiple different hospitalization or emergency encounters							
N/A = Not Applicable							

Table 4b: Summary of Diagnosis Identification and Review

Event	Automated Algorithm			Physician Review			Diagnosis is continuation of an ongoing episode (g)	Diagnosis is a recurrence (h)	Total Diagnoses for Analysis (i=a-b-e-f-g)
	Potential diagnoses identified (a)	Excluded diagnoses based on pre-existing condition (b)	Diagnoses remaining from automated algorithm identification (c=a-b)	Diagnoses confirmed (d)	Diagnoses refuted (e)	Confirmed events with diagnosis determined to be prior to index vaccination (f)			
Specific diagnoses									
diagnosis 1									
diagnosis 2									
Diagnosis groupings									
grouping 1									
grouping 2									
Number of recipients experiencing a single diagnosis									
Number of recipients experiencing multiple different diagnoses									

N/A = Not Applicable

Table 5a: Frequency and rate of hospitalization and emergency events observed following vaccination with MenACWY-CRM

Event	Overall		Number of vaccines received prior to event							
			One		Two		Three		Four	
	Frequency n (%)	Rate (95% CI)*	Frequency n (%)	Rate (95% CI)*	Frequency n (%)	Rate (95% CI)*	Frequency n (%)	Rate (95% CI)*	Frequency n (%)	Rate (95% CI)*
Hospitalization only										
Emergency department only										
Emergency department and hospitalization										

*Events per 1000 person years

Table 5b: Frequency and rate of diagnoses observed following vaccination with MenACWY-CRM

Event	Overall		Number of vaccines received prior to event								Setting of initial presentation with the diagnosis*						First occurrence or recurrence			
			One		Two		Three		Four		Inpatient		Emergency		Both settings		First occurrence		Recurrence	
	Frequency n (%)	Rate (95% CI)*	Frequency n (%)	Rate (95% CI)*	Frequency n (%)	Rate (95% CI)*	Frequency n (%)	Rate (95% CI)*	Frequency n (%)	Rate (95% CI)*	Frequency n (%)	Rate (95% CI)*	Frequency n (%)	Rate (95% CI)*	Frequency n (%)	Rate (95% CI)*	Frequency n (%)	Rate (95% CI)*	Frequency n (%)	Rate (95% CI)*
Specific diagnoses																				
diagnosis 1																				
diagnosis 2																				
Diagnosis groupings																				
grouping 1																				
grouping 2																				
etc.																				

*Events per 1000 person years

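### An illness that began before dose 2, 3 or 4 can be credited to that dose, because events are placed by date and earlier onset is reviewed only against the first dose

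*SAP*

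**What the plan says.** The rules for placing an event are in SAP v2.0, section 5.2. "Person-time for each dose will begin at the date of vaccination", and the last of the listed end points for each dose's person-time is "receipt of an additional dose of MenACWY-CRM, whichever comes first". For encounters, "the encounter date will be used to determine the timing of the encounter relative to the timing of vaccine dose". For diagnoses, "the first diagnosis date for each diagnosis in any care setting will be used to determine the timing of the diagnosis". SAP 3.3.3 times an event from the most recent dose. No rule orders a dose and an event that fall on the same date.

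The checks for earlier disease all look back from the first dose. The automated search in SAP 5.1 stops there. Under Protocol 9.8.1, chart review decides whether the condition came before the child's first MenACWY-CRM dose. The matching physician-review column in Tables 4a and 4b is "Confirmed events with diagnosis determined to be prior to index vaccination (f", that is, column (f).

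One rule does protect later doses. In the SAP Definitions, under Episode: "For each episode, the first diagnosis date in any care setting will be used for analyses".

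Protocol 9.3 (Setting) describes "a policy of vaccinating at all visits, not just well child or physical exam appointments". SAP 5.4 plans no sensitivity analysis.

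**The concern.** Under that site policy a child can receive a dose at a visit made because of illness. If dose 2 is given at such a visit, the illness came before the injection, but its first code carries the dose-2 date. A later ED visit in the same illness carries a date inside the dose-2 window. No planned field asks whether the illness came before dose 2, so nothing moves it back to dose 1.

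What is at stake is the dose-specific description: the rates by number of doses in Tables 5a and 5b, and the dose distribution and age at most recent vaccination in Table 6. With few children, one misplaced event visibly changes a dose stratum.

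**Working it through.** **The plan's own figure.** The only computed figures are the expected confidence intervals in SAP 3.2. For x events in T person-years, the exact Poisson 95% limits are χ²(0.025; 2x)/(2T) and χ²(0.975; 2x+2)/(2T). At 10 per 100 person-years and N=100, x=10 and T=100. This gives 4.795 to 18.390 per 100 person-years; the SAP prints 4.8 to 18.4. All 12 cells agree to within 0.1. The table is sound and the point does not depend on it.

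**The rules applied to dose 2** (doses 3 and 4 likewise):

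| Sequence | Diagnosis analysis (Tables 5b, 6) | Encounter analysis (Table 5a) |
|---|---|---|
| Illness coded in clinic before the dose date; ED visit after the dose | Previous dose, by the episode rule | Later dose |
| Illness first coded at the visit where the dose is given; ED visit three days later, same episode | Carries the dose date; can go to the later dose | Later dose, at day 3 |
| ED visit, then the dose later on the same date; illness first coded in the ED | Same date, no rule; can go to the later dose | Same date, no rule; can go to the later dose |

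For dose 1, physician review and column (f) can remove a condition that preceded the injection. Doses 2 to 4 have no counterpart.

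**Size of one misplaced event.** Inputs:
- 60 to 100 children with high-risk conditions (SAP 3.2).
- A 2-month window, the interval from dose 2 to dose 3 in the 2, 4, 6, 12 month series (SAP 3.3.2), and the full 6-month window.
- Assumption: every child reaches the dose and stays under observation for the whole window.

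Effect on the dose's rate = 1000 / (N × months / 12) per 1000 person-years.
- 2 months: 60 × 2/12 = 10.0 and 100 × 2/12 = 16.7 person-years, so one event adds 100 or 60.
- 6 months: 60 × 6/12 = 30 and 100 × 6/12 = 50 person-years, so one event adds 33 or 20.
- Table 6 admits diagnoses with at least five episodes. At five, one misplaced episode shifts the dose distribution by 1/5 = 20 percentage points.

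**Overall rate.** If the previous window was still open at onset, the event only changes stratum and the total is the same. If it had closed, the total is one event too high. At the SAP's average of one person-year per child, that is 1000/100 = 10 to 1000/60 = 16.7 per 1000 person-years. Such a gap is possible: Protocol 9.3.1 cites doses at 6 months and at 12 through 15 months of age. These are 6 to 9 months apart, which leaves up to 3 months outside any window.

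**The case against.** The strongest reply is that the plan is silent on same-date events, not wrong about them. SAP 3.3.3 times an event from a later dose where the event occurred after that dose was administered. Read literally, a morning ED visit before an afternoon dose does not qualify. This stands, and it is why the point says such events can be credited to the later dose, not that they will be. It does not help with an ED visit after the dose for an illness that was already present.

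The episode rule also stands as a real safeguard. In the diagnosis analysis, an illness coded on any earlier day keeps its earlier date. The encounter analysis has no such rule.

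The study is descriptive, dose strata are shown only if numbers allow, and the intervals are wide. With 10 person-years, 4 events give 400 per 1000 person-years (exact 95% interval 109 to 1024) and 5 give 500 (162 to 1167). One event is therefore small beside the sampling error. But the error is avoidable and always favours the later dose, and the interval does not reflect it.

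A reader might infer a contradiction with Appendix B, which counts indication codes from "six months prior to index vaccination, including the date of index vaccination". That rule identifies the reason for vaccination and serves a different purpose from outcome exclusion. It shows only that same-day handling should be stated for the outcome too.

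**Conclusion.** The point holds for doses 2 to 4 as a gap in dose attribution. It covers an illness first coded at the visit where a later dose was given, an ED visit earlier on the same date, and, in the encounter analysis, an ED visit after the dose for an illness that began before it. The effect is on dose-stratified results. The overall rate is affected only where the previous 6-month window had closed.

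The documents give no frequency. The 60 to 100 per 1000 person-years is the effect of one event in a 2-month window, assuming that every child reaches that dose. Real strata would be smaller and the effect of one event larger.

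A reader might go further and infer an artificial peak of Day 0 reactions. The documents do not support that. Day 0 is defined only for the index vaccination, no table shell shows days since dose, and an ED visit three days after a dose is a day 3 encounter. Sizing such a peak would need the share of doses given at sick visits and the share of those illnesses that reach the ED, and the documents give neither. This is a cheap improvement, not a flaw in the overall estimate.

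**What to change.** In SAP 5.1 and 5.2:

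- For each event assigned to dose 2, 3 or 4, have the physician review record whether the illness or encounter began before that dose was given: yes, no or unclear.
- If yes, assign the event to the previous dose's window, provided that window was still open on the onset or encounter date. Otherwise exclude it as not within 6 months of a prior dose.
- If unclear, keep it with the later dose and flag it.
- Keep column (f) as an index-dose exclusion, and state that it includes same-day conditions that preceded the injection. Do not extend it to every dose. It is subtracted from the totals (Table 4a: g=a-b-e-f; Table 4b: i=a-b-e-f-g), so extending it would delete valid events that began after dose 1 and before dose 2.
- Add to Tables 4a and 4b a separate count, not subtracted, of events reassigned between doses.

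The cost is SAP wording, one review field and one table column. SAP 3.1 already has a physician review all identified events, so no new data source is needed. The downside is that the order of events, or onset, may be unclear in a few charts.

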3.3.2 Exposure

MenACWY-CRM vaccination will be received as part of routine clinical care. All vaccinations are documented in the EMR at time of administration. This study is strictly observational. MenACWY-CRM will be the only meningococcal vaccine used in children 2-23 months of age to prevent *N. meningitidis* serogroup A, C, W135 and Y caused meningococcal disease in KPSC. While other meningococcal vaccines are available for vaccination of KPSC members over 23 months of age, each vaccine has a unique identifier in the KPSC electronic databases and is therefore distinguishable.

In infants initiating vaccination at 2 months of age, MenACWY-CRM is to be administered as a four-dose series at 2, 4, 6, and 12 months of age. Among children 7-23 months of age who have not previously received a dose of MenACWY-CRM, MenACWY-CRM is to be administered as a two-dose series with the second dose administered in the second year of life and at least three months after the first dose. While health care providers (HCP) are advised to follow the ACIP Recommended Childhood Vaccine schedule, vaccination decisions will be determined by the treating HCP and the caregivers.

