3.3.3 Outcomes

Outcomes include medical events that require ED visits or hospitalizations in children 2-23 months of age following any dose of MenACWY-CRM vaccination. Medical events occurring in ED and inpatient settings within 6 months following a MenACWY-CRM vaccination will be searched in the EMR. Evidence of the same pre-existing medical event (based on ICD diagnosis code) will be searched for in all care settings (inpatient, outpatient, or ED) prior to the first dose of MenACWY-CRM vaccination.

Events with a history of the same diagnosis prior to the first dose of MenACWY-CRM vaccination will be excluded as a pre-existing condition. The medical records prior to the first dose of MenACWY-CRM will be searched for the same diagnosis code. As there will be a transition from International Classification of Diseases, Ninth Revision (ICD-9) to Tenth Revision (ICD-10) coding, in the event that the diagnosis following a MenACWY-CRM vaccination is coded using ICD-10, both the same ICD-10 code and an equivalent ICD-9 diagnosis code will be searched in the period prior to the first dose.

If a study subject is first seen in the ED and subsequently transferred to the hospital, this will be treated as a single event.

For each identified ED or inpatient visit the following information will be collected:

- Diagnosis of medical events
- Date of diagnosis: the date of the documented code after any dose of MenACWY-CRM vaccination is considered the date of diagnosis. The date of diagnosis is expressed as the number of days following the 1st, 2nd, 3rd, or 4th dose of MenACWY-CRM vaccination.
- Health care setting: hospitalization or ED or both
- First occurrence vs. recurrence of the diagnosis

One subject can experience multiple different events. In the specific situation where an eligible child received multiple doses during the observation period and the event occurred after the administration of a later dose, the timing of the event is calculated from the date of administration of the most recent dose. In the case of a recurrence of the same condition, the initial diagnosis and the recurrent diagnosis will each be separately described relative to the most recent dose.

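### By-dose rates in Tables 5a and 5b rest on windows of unequal length (about 2, 2, 6 and 6 months in the four-dose series), so early-clustered events can appear to differ by dose through window length alone; add a common early-window rate

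*SAP*

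**What the plan says.** SAP v2.0, section 5.2, sets the per-dose denominator: "Person-time for each dose will begin at the date of vaccination and end at 6 months following vaccination", or earlier at disenrollment, death, "the end of data collection, or receipt of an additional dose of MenACWY-CRM, whichever comes first". The SAP definition of the observation period and protocol section 9.7.3 give the same rule. Under SAP section 3.3.3, for a child with several doses, "the timing of the event is calculated from the date of administration of the most recent dose".

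SAP section 3.3.2 states two schedules. For infants starting at 2 months, "MenACWY-CRM is to be administered as a four-dose series at 2, 4, 6, and 12 months of age". For children starting at 7-23 months it is a "two-dose series with the second dose administered in the second year of life and at least three months after the first dose".

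On reporting, section 5.2 says "The rate and Poisson 95% confidence interval of the rate of medical events will be calculated and presented as number per 1000 person-years", and "If the number of medical events allows, captured medical events will be stratified by dose". Table shells 5a and 5b set the rates side by side in columns One to Four under the label "Number of vaccines received prior to event".

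The plan has no common risk window for the dose columns and no table of rates by time since dose. Section 5.4 plans no sensitivity analysis, and the limitations in section 6.2 do not mention unequal windows.

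**The concern.** Dividing by person-time makes windows of different length comparable only if the event rate is constant over the window. Risk caused by a vaccine need not behave that way; it may sit in the first days or weeks. The same number of early events is then divided by about 2 months after doses 1 and 2 of the infant series, and by 6 months after doses 3 and 4.

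The study has no unvaccinated group, so the dose columns are its only contrast by exposure, and readers will look across them. Window length alone could make later doses look safer than earlier ones. It could also flatten or reverse a real increase with later doses. The Poisson interval reflects sampling error only and gives no warning of this.

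**Working it through.** **The plan's own figure.** The documents give no per-dose window or rate. The only computed figure is the precision table in SAP section 3.2. Exact Poisson limits with d = rate × person-years reproduce all 12 cells to rounding. For example, 10 per 100 person-years with N = 100 gives d = 10 and limits of 4.8-18.4, as printed. That table concerns overall rates and does not bear on the dose columns.

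**Step 1: windows.** Window after a dose = min(6 months, gap to next dose).

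| Schedule | Windows (months) |
|---|---|
| Doses at 2, 4, 6, 12 months | 2, 2, 6, 6 |
| Fourth dose at 15 months (range in protocol 9.3.1) | 2, 2, 6, 6 |
| Two doses, at least 3 months apart | 3 to 6, then 6 |
| One dose only | 6 |

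**Step 2: rates in four-dose children.** Let q be the acute risk per dose, the same after every dose and falling within 2 months. Let b be a constant background per 1000 person-years. Then rate = 1000q/(m/12) + b for a window of m months. The documents give neither q nor b, so the values below are assumptions.

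| q | b | 2-month window | 6-month window | Ratio |
|---|---|---|---|---|
| any | 0 | 6000q + 0 | 2000q + 0 | 3.0 |
| 1% | 300 | 60 + 300 = 360 | 20 + 300 = 320 | 1.1 |
| 5% | 300 | 300 + 300 = 600 | 100 + 300 = 400 | 1.5 |
| 10% | 300 | 600 + 300 = 900 | 200 + 300 = 500 | 1.8 |
| 5% | 10 | 310 | 110 | 2.8 |
| 5% | 1000 | 1300 | 1100 | 1.2 |
| 0 | any | b | b | 1.0 |

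The ratio also shrinks if the risk is spread out. With no background, risk spread evenly over 3, 4 or 6 months gives 2.0, 1.5 or 1.0.

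**Step 3: masking.** Take b = 300 and q = 5% after early doses (rate 600). If q doubles to 10% after later doses, the later rate is 200 + 300 = 500, an apparent fall. If it triples to 15%, the later rate is 300 + 300 = 600, apparently flat.

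**Step 4: mixing of schedules.** Let p be the share of recipients on the four-dose series (not in the documents), with no background and the same share in both columns. The mean window is 2p + w(1 − p), with w = 3 to 6 months in column One and 6 in column Two. At p = 0.5 the mean is 2.5 to 4 months in column One and 4 in column Two, so the ratios to a 6-month window are 2.4 to 1.5 and 1.5. At p = 0.25 they are 2.2 to 1.2 and 1.2. On schedule, columns Three and Four hold four-dose children only.

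**Step 5: a common window.** With days 0-55 the window is 56/365.25 = 0.153 years after every dose. At q = 5% (all within the window) and b = 300, the rate is 0.05/0.153 × 1000 + 300, about 626, after each dose. The part due to window length is gone.

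**The case against.** Several objections are sound and limit the point.

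- **Scope.** The 2-month windows belong to the four-dose series only. Two-dose and single-dose children lengthen the average window in columns One and Two. This dilutes the contrast but does not reverse it.
- **Mechanism.** The outcome is any eligible emergency or inpatient event, not a reaction. Under a constant hazard person-time does its job. Protocol section 7.0 reports that serious events in trials were similar with and without the vaccine, so a large acute risk should not be presumed.
- **Precision.** SAP section 3.2 expects 60-100 children with high-risk conditions. Suppose 50 complete four doses, with q = 5% and b = 300. Dose 1 then has 50 × (0.05 + 0.05) = 5 expected events, a rate of 600 (exact 95% interval 195-1400). Dose 3 has 50 × (0.05 + 0.15) = 10 events, a rate of 400 (192-736). A ratio of 1.5 cannot be read from such data.
- **No test planned.** The study is descriptive, the dose columns appear only if numbers allow, and Table 3 shows the days between doses.

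What survives is that rates with intervals are to be printed by dose, side by side and without a caveat, on a definition that is not comparable for early-clustered events. Imprecision does not make the definition right. In the 50-child example, the count doubles from dose 1 to dose 3 while the rate falls by a third, although neither the acute risk nor the background rate has changed.

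**Conclusion.** The point holds as a conditional one. Where risk is concentrated soon after a dose, the by-dose rates in Tables 5a and 5b can differ through window length alone. The ceiling is a ratio of 3.0, which needs four-dose children only, risk confined to the first 2 months, and no background. With an assumed background of 300 per 1000 person-years it is about 1.1 to 1.8 for assumed acute risks of 1% to 10% per dose. It matters mainly for specific diagnoses with low background in Table 5b, and less for the all-cause encounters in Table 5a.

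Two stronger readings are not supported. A reader might infer that the tables will show a falling, even threefold lower, rate after later doses. That needs an acute risk and a schedule mix that the documents do not give, and a constant hazard yields no distortion. A reader might also infer that a common window would make the columns equal whenever the vaccine effect is equal. It would not: the infant series gives doses 1-2 at 2 and 4 months of age and doses 3-4 at 6 and 12 months, so any age trend in emergency or hospital use would remain.

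This is a cheap improvement to reporting, not a defect in the overall rate.

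**What to change.** Keep the by-dose rates defined in the protocol, and the Overall column, as they are. Add to Tables 5a and 5b a supplementary by-dose rate over one common early window no longer than the shortest scheduled gap, for example days 0-55. Restrict both events and person-time to that window, and still cut at the next dose, disenrollment, death or end of data collection. State that day 0 here is the date of the dose concerned, because the SAP definition of Day 0 refers only to the index vaccination. Use the event dates that section 5.2 already sets for encounters and diagnoses.

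Add a footnote that the full-window by-dose rates cover unequal windows and that age differs between doses.

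The cost is a short SAP addition and one program cut; SAP section 3.3.3 already collects days since dose. Replacing the by-dose rate instead would contradict protocol section 9.7.3, require an amendment under protocol section 10.5, and discard about two-thirds of the person-time after doses 3 and 4. The drawback is sparse data. In the 50-child example the common window holds 2.5 + 50 × 0.153 × 0.3 = about 4.8 expected events per dose, so intervals will be wide and some cells will fall below the n ≥ 5 display rule.
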